9.3. Exploratory Analyses

9.3.1. FXR Activity

FXR activity will be assessed by measuring FGF-19. This parameter will be analyzed using arithmetic summary statistics, ANCOVA, and model estimates with independent variables as described in [Section 6.2.3](#) for the primary efficacy endpoint.

10. SAFETY ANALYSES

All safety analyses will be based on the Safety Population. The evaluation of the effects of OCA on safety parameters in the PSC population is a primary objective of this study.

10.1. Extent of Exposure

10.1.1. Investigational Product (OCA or Placebo)

Subjects will titrate their dose of OCA or placebo at the Week 12 visit according to the criteria specified in the protocol. Frequency counts and percentages of the number of subjects who do not up-titrated will be summarized. The duration of investigational product exposure will be calculated as follows:

- Exposure to investigational product = $\{[(\text{Date of last investigational product dose} - \text{Date of 1st investigational product dose}) + 1] - \text{Total duration of temporary investigational product discontinuation}\}$

The duration of each incidence of temporary investigational product discontinuation will be calculated as follows:

- Duration of temporary discontinuation of investigational product = $(\text{Date of restart of investigational product} - \text{Date of temporary discontinuation of investigational product}) + 1$.

The total duration of temporary investigational product discontinuation is the sum duration of temporary discontinuation of investigational product over each incidence of discontinuation.

Total investigational product (mg) exposed to subject will be calculated by adding the doses taken by a subject during the study and will be summarized using descriptive statistics.

Subject's overall compliance (%) with investigational product will be calculated as follows:

- $(\# \text{ of days consumed during study}) / (\# \text{ of days on study drug, excluding drug holidays}) * 100$

Investigational product compliance will be summarized by treatment group using descriptive statistics.

Additional summaries will present the number and percentage of subjects with any drug interruption, subjects with alternate dosing, subjects with reduced dose, subjects who did not titrate dose at Week 12, and number of subjects with permanent discontinuation. Denominators for calculating percentages will be based on the number of subjects who received at least one

dose in the treatment group summarized. All exposure data will be presented in a subject data listing.

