- Dose frequency modification: Less frequent dosing of investigational product (eg, on alternate days) may be tried, after which subjects may return to their original daily dose, if and as tolerated.
- Drug holiday: A drug holiday is defined as an Investigator ‘prescribed’ complete interruption of dosing for 1 or more consecutive days (ie, non-daily dosing does not constitute a drug holiday). For subjects with severe pruritus, instruct the subject to stop taking investigational product until the pruritus subsides to an acceptable level at which time it should be restarted (likely, on a modified, alternate day dosing schedule). Details of drug holidays and/or nondaily dosing regimens should be recorded in the CRF. Such cases should be discussed with the Medical Monitor.
- Other therapies may be tried as deemed clinically appropriate.

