6.3.5. Standard Calculations

Variables requiring calculation will be derived using the following formulas:

- **Days:** A duration expressed in days between one date (*date1*) and another later date (*date2*) will be calculated using the following formulas:

$$\text{duration (days)} = \text{date2} - \text{date1} + 1$$

- **Months:** A duration expressed in months is calculated as the number of days divided by 365.25 / 12.

- **Years**—A duration expressed in years between one date (*date1*) and another date (*date2*) is calculated using the following formulas:

$$\text{duration (years)} = (\text{date2} - \text{date1} + 1) / 365.25$$

- **Age**—Age is calculated as the number of years from the date of birth (*DOB*) to the specified date, eg, date of informed consent (*DOIC*). If the month of DOIC < month of DOB or the month of DOIC=DOB and the day of DOIC < day of DOB, then the following formula is used:

$$\text{age (years)} = \text{year of DOIC} - \text{year of DOB} - 1.$$

Otherwise, the following formula is used:

$$\text{age (years)} = \text{year of DOIC} - \text{year of DOB}.$$

- **Height:** Height measured in inches (in) are converted to centimeters (cm) using the following formula:

$$\text{height (cm)} = \text{height (in)} \times 2.54$$

- **Weight:** Weight measured in pounds (lb) are converted to kilograms (kg) using the following formula:

$$\text{weight (kg)} = \text{weight (lb)} / 2.2046$$

- **Temperature:** Temperature measured in degrees Fahrenheit are converted to degrees centigrade using the following formula:

$$\text{temp (degrees centigrade)} = 5 / 9 \times (\text{temp [degrees Fahrenheit]} - 32)$$

- **Body Mass Index (BMI):** BMI is calculated using height (cm) and weight (kg) using the following formula:

$$\text{BMI (kg/m}^2\text{)} = \text{weight (kg)} / ([\text{height (cm)} / 100]^2)$$

- **Change from Baseline:** Change from Baseline is calculated as:

$$\text{change from Baseline} = \text{DB post-Baseline value} - \text{Baseline value}$$

- **Percentage change from Baseline:** Percentage change from Baseline is calculated as:

$$\text{percentage change from Baseline} = 100 \times ([\text{DB post-Baseline value} - \text{Baseline value}] / \text{Baseline value})$$

- **Geometric mean** - In order to calculate a geometric mean and corresponding 95% CI, the following steps are used:

- Transform the data by taking natural logarithms (\log_e)

- Calculate the mean and 95% CI of the \log_e -transformed data

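### The SAP's formula for a temporary discontinuation counts the restart day as off drug, so net exposure is understated by 1 or 2 days per interruption

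*SAP*

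**What the plan says.** SAP 10.1.1 builds exposure duration in two layers. The outer layer is the last dose date minus the first dose date, plus 1. From this it subtracts the total time off drug. The inner layer defines "Duration of temporary discontinuation of investigational product" for each episode: it starts from the "Date of restart of investigational product", subtracts the date of temporary discontinuation, and adds 1. The total "is the sum duration of temporary discontinuation of investigational product over each incidence of discontinuation".

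SAP 6.3.5 sets the same pattern as the general rule for durations in days: later date minus earlier date, plus 1.

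Protocol 11.1.3.1, in the pruritus guidance after Table 9, defines a drug holiday as an investigator-prescribed "complete interruption of dosing for 1 or more consecutive days" and asks for the details to be recorded in the CRF. Neither document says whether the discontinuation date is the last day a dose was taken or the first day a dose was missed.

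**The concern.** Adding 1 to a difference of dates is right only when both end dates belong to the interval being counted. That is true of the outer layer, because the first and last dose dates are both days on drug. It is not true of the inner layer, because on the restart date the subject is taking drug again. That day is counted once as exposure in the outer term and then removed as time off drug.

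Because the total is taken over every episode, the error always runs in the same direction and grows with the number of interruptions. Exposure is reported under the safety analyses, and safety is one of the trial's two primary objectives, so the duration should be correct even though it is only descriptive.

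**Working it through.** The documents give no numerical result here, so there is no figure to reproduce. The check is a direct count of days.

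**Inputs**
- Dosing is once daily for two 12-week periods (SAP 3): 2 × 12 × 7 = 168 days, taken as Days 1 to 168.
- Gross exposure (SAP 10.1.1): 168 − 1 + 1 = 168 days.
- SAP duration of one interruption: restart − discontinuation + 1.
- Reading A: the discontinuation date is the first missed day.
- Reading B: the discontinuation date is the last day on which a dose was taken.
- The gap lengths and positions below are illustrative.

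**One 7-day gap.** Days 50 to 56 are missed, the last dose before the gap is on Day 49, and the restart is on Day 57.
- True time off drug: 56 − 50 + 1 = 7; true exposure: 168 − 7 = 161.
- Reading A: 57 − 50 + 1 = 8; exposure 168 − 8 = 160.
- Reading B: 57 − 49 + 1 = 9; exposure 168 − 9 = 159.

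Other patterns, by the same method (days off / days exposed):

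| Pattern | True | SAP, reading A | SAP, reading B |
|---|---|---|---|
| One 1-day gap | 1 / 167 | 2 / 166 | 3 / 165 |
| One 7-day gap | 7 / 161 | 8 / 160 | 9 / 159 |
| One 14-day gap | 14 / 154 | 15 / 153 | 16 / 152 |
| Three 7-day gaps | 21 / 147 | 24 / 144 | 27 / 141 |

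The excess depends on the number of interruptions, not their length: 1 day each under A, 2 days each under B. Per interruption that is 1/168 = 0.6% or 2/168 = 1.2% of the course.

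**Check against the protocol's shortest holiday.** A restart must fall after the discontinuation date, so the difference is at least 1 and the SAP formula returns at least 2. It can never return the one-day interruption that Protocol 11.1.3.1 allows.

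**Where the quantity is used**
- Total mg is obtained by adding the doses taken (SAP 10.1.1), so it is unaffected.
- Pruritus event days per patient-year use the last known date and the first dose date (SAP 10.3.1), without subtracting interruptions.
- Exposure-response plots use plasma AUC over 0 to 6 hours (SAP 9.2.5).
- Adverse event tables are based on subject incidence (SAP 10.2), not on rates per day exposed.
- The compliance denominator excludes drug holidays (SAP 10.1.1), but the SAP does not say that it reuses this total. If it does, a subject who took every dose outside the holiday would exceed 100%. One 7-day gap gives 161/160 = 100.6% under A; three give 147/144 = 102.1%.

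**The case against.** The strongest defence is that the formula follows the SAP's own convention in 6.3.5 and that the eCRF is not among the documents. If the restart field in practice held the last day off drug, and the other field the first missed day, the inclusive count would be exact. This cannot be ruled out without the eCRF, but it runs against the plain meaning of a restart date, and nothing in either document supports it. The general rule explains where the added day probably came from; it does not make it right for an interval that ends on a dosing day.

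The eCRF point does limit what can be said about size. The 1-day excess follows from the restart date alone. The 2-day excess needs the further condition that the discontinuation date is the last dose taken.

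A reader might also infer that OCA exposure will be understated more than placebo exposure, because Protocol 4.4 and 4.5 describe drug- and dose-related pruritus in PBC and expect similar results in PSC. The documents do not establish this. They give no interruption rates by arm. Protocol 7.4.2 calls pruritus less common in PSC than in PBC, and also permits interruption for bacterial cholangitis (anticipated in 10% to 15% of subjects) and for bile duct stricture, neither of which is stated to be specific to OCA. Less frequent dosing is expressly not a drug holiday under Protocol 11.1.3.1.

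Nor should the loss be enlarged by assuming many single-day holidays in one subject. No passage describes that pattern; the guidance for severe pruritus is to stop until it subsides to an acceptable level and then restart.

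**Conclusion.** The formula is wrong as written, and no other section corrects it. Each interruption is too long by 1 day if the discontinuation date is the first missed dose, or by 2 days if it is the last dose taken. Net exposure is understated by the same amount: 0.6% to 1.2% of 168 days per interruption. This assumes once-daily dosing and that the restart date is the first day back on drug.

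The consequence is minor. It reaches the descriptive exposure duration, and compliance only if the denominator shares the total. No efficacy test, sample-size figure, total dose or pruritus rate depends on it. A difference between arms is possible if interruption rates differ, but the documents do not allow it to be sized or its direction stated as fact.

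**What to change.** In SAP 10.1.1, state which date the eCRF holds as the discontinuation date, and then use the matching formula:
- first missed dose recorded: restart date − first missed dose date, with no added day;
- last dose taken recorded: restart date − last dose date − 1.

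For the 7-day gap above these give 57 − 50 = 7 and 57 − 49 − 1 = 7, leaving 161 days exposed. For three such gaps, both give 21 days off and 147 exposed. The outer first-to-last-dose count stays as it is.

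Also say whether the compliance denominator uses the same corrected total. The cost is a one-line change to the SAP and the matching derivation. It needs no new data beyond the two dates the formula already uses, and it does not alter how subjects are managed.

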#### Secondary

To evaluate the effects of OCA on the following in subjects with PSC:

- Hepatic biochemistry and indices of function
- Markers of:
  - Hepatic fibrosis and GI inflammation and disease
  - Farnesoid X receptor (FXR) activity
  - Inflammatory bowel disease (IBD)
- Pharmacokinetics (PK) of OCA and other bile acids
- Exposure response of total OCA (OCA and its conjugates) to biomarkers (eg, ALP and bile acids)
- Long-term efficacy and safety of OCA
- Disease-specific symptoms.

**Methodology:***Double-blind Phase (DB)*

This is a Phase 2, randomized, double-blind, placebo-controlled, dose-finding evaluation of the efficacy and safety of OCA in subjects with PSC. Approximately 75 subjects who provide written informed consent and meet all of the inclusion and none of the exclusion criteria will be randomized to 1 of 3 treatment groups as follows: 1.5 mg titrating to 3 mg OCA, 5 mg titrating to 10 mg OCA, or placebo, in a 1:1:1 ratio. Subjects will administer investigational product orally, once daily for 2 consecutive 12-week periods.

For the first 12 weeks, the subject's dose will be 1.5 mg OCA, 5 mg OCA, or placebo. After 12 weeks, the subject's dose will be titrated as follows, providing there are no limiting safety or tolerability concerns in the opinion of the Investigator, while maintaining the trial blind: the 1.5 mg OCA treatment group will titrate to 3 mg, the 5 mg OCA treatment group will titrate to 10 mg OCA, and the placebo group will remain on placebo. DB treatment will continue for a further 12 weeks at that dose.

Any subjects whose dose is not titrated, due to safety or tolerability concerns, will remain on their starting treatment (1.5 mg OCA, 5 mg OCA, or placebo) for the remainder of the DB phase to Week 24.

Randomization will be stratified by the presence or absence of concomitant ursodeoxycholic acid (UDCA) use and total bilirubin level ( $\leq 1.5x$  upper limit of normal [ULN] or  $>1.5x$  ULN but  $<2.5x$  ULN).

*Long-Term Safety Extension Phase (LTSE)*

Following completion of participation in the DB phase, subjects will be asked to reconfirm their consent for participation in the open-label long-term safety extension (LTSE) phase (a further 24 months).

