### 8.3. Treatment Compliance

The Investigator should assess the subject's compliance with dosing of investigational product on an ongoing basis and at each contact and onsite visit; this should be confirmed by conducting drug accountability (ie, count of returned tablets) during subjects' on site visits.

Subjects should be instructed to retain all bottles of investigational product, even if empty, and to return them to the Investigator at the subsequent visit. The Investigator or designee should

perform drug accountability and, if applicable, follow up with the subject to retrieve any investigational product bottles that have not been returned.

If the Investigator has concerns about a subject's dosing compliance she/he should discuss this with the subject, assess the reasons for noncompliance and the likelihood that the subject will remain noncompliant, and notify the Sponsor accordingly. Continued trial eligibility should be assessed.

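### The SAP compliance formula marks down subjects who correctly follow permitted alternate-day dosing, and it does not say how a partly taken daily dose is scored

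*SAP*

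**What the plan says.** SAP 10.1.1 gives one overall compliance percentage per subject, summarised by treatment group. It is the number "of days consumed during study}) / (\# \text{ of days on study drug, excluding drug holidays}) * 100". Neither the numerator nor the denominator is defined further. The same section also plans a summary of total mg taken, counts of subjects with interruption, alternate dosing, reduced dose and no Week 12 titration, and a subject listing of all exposure data.

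The protocol's default regimen is daily: "Subjects will administer investigational product orally, once daily for 2 consecutive 12-week periods". For pruritus, Protocol 11.1.3.1 adds an option: "Less frequent dosing of investigational product (eg, on alternate days) may be tried". It defines a drug holiday as a complete interruption prescribed by the Investigator and states that "non-daily dosing does not constitute a drug holiday". Holidays and non-daily regimens are both to be recorded in the CRF.

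The daily dose is two tablets to Week 12 and four afterwards (Protocol 8.1, Table 6). Each OCA arm takes active tablets of one size and placebo tablets of the other. Protocol 8.3 has sites confirm compliance by counting returned tablets. Protocol Table 1 schedules this accountability at Weeks 2, 6, 12, 14, 18 and 24.

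**The concern.** The formula treats two Investigator-directed measures differently. A prescribed holiday is removed from the denominator. A prescribed alternate-day schedule, which Protocol 11.1.3.1 describes as the likely way of restarting after a holiday, is not, so each prescribed off-day counts against the subject.

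The error may not fall evenly across arms. Protocol 4.5 describes a dose-dependent worsening of pruritus with OCA in PBC and expects similar results in PSC. If alternate-day dosing follows that pattern, reported compliance would fall most in the 5-to-10 mg arm even with every instruction followed.

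The numerator raises a separate problem. A day count cannot distinguish a full dose from part of one, and the tablet number doubles at Week 12, when the dose tested in the primary comparison begins. Readers of a dose-finding trial will look to this table to judge whether the planned dose was taken.

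**Working it through.** The plan states no compliance figure, so there is none to reproduce. The check applies the SAP formula by direct count.

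**Inputs.** The double-blind phase is 2 × 84 = 168 days (Protocol synopsis and 6.1). Tablets prescribed are 84 × 2 + 84 × 4 = 504 (Protocol 8.1). For the 5-to-10 mg arm, planned OCA is 84 × 5 + 84 × 10 = 1260 mg (Table 6).

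**1. Alternate-day dosing, followed exactly.** With A days on that regimen, A/2 are off-days. None is a drug holiday, so the denominator stays at 168. The score is 100 × (168 − A/2)/168 = 100 × (1 − f/2), with f = A/168.

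| Weeks on alternate days | A | Days dosed / 168 | Score |
|---|---|---|---|
| 2 | 14 | 161/168 | 95.8% |
| 6 | 42 | 147/168 | 87.5% |
| 12 | 84 | 126/168 | 75.0% |
| 22 | 154 | 91/168 | 54.2% |
| 24 | 168 | 84/168 | 50.0% |

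Adherence to the prescribed regimen is 100% in every row.

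**2. Effect on an arm mean.** The documents give no frequency of alternate-day dosing, so the proportion p is an assumption. If a proportion p of an arm alternates for 12 weeks and nothing else differs, the mean falls by p × 25 points: 2.5 points at p = 10%, 5 points at p = 20%.

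**3. Part of the dose taken every day.** This step assumes that a day counts as consumed when any tablet is taken. Take a 5-to-10 mg subject who, from Week 12, takes one of the two big tablets and both small ones each day.

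| Measure | Weeks 12–24 | Overall |
|---|---|---|
| SAP formula | 84/84 = 100% | 168/168 = 100% |
| Active dose | 420/840 mg = 50% | 840/1260 mg = 67% |
| All tablets pooled | 252/336 = 75% | 420/504 = 83% |
| Big tablets only | 84/168 = 50% | 168/252 = 67% |

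A subject who takes half of all tablets each day (252 of 504) also scores 100%. Under the double-dummy, the OCA taken could lie anywhere from 0 to 1260 mg.

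**4. The same cases under a tablet ratio.** Alternate-day dosing throughout, fully followed, prescribes 42 × 2 + 42 × 4 = 252 tablets. With all 252 taken, the score is 100%. For the subject in step 3, the big-tablet ratio matches the active dose, whereas the pooled ratio overstates it.

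**The case against.** The strongest reply is that the formula's two terms are undefined, so neither result is certain. If days on study drug meant days on which a dose was due, alternate-day dosing would score 100%. If a day counted only when the full dose was taken, days of partial dosing would score zero. The second point stands: the 100% score for partial dosing is what the text allows, not what it dictates. The first is weaker. The SAP does not state that meaning, and it would make the explicit exclusion of drug holidays unnecessary.

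A second reply is that the section already plans summaries of total mg, alternate dosing and reduced dose. A reader might infer that the plan conceals under-dosing after titration. The documents do not support that, because these summaries and the exposure listing would show much of it. They are only a partial offset, however. Total mg has no prescribed amount beside it, so it cannot separate missed tablets from withdrawal, holidays, non-titration or a changed regimen. It also says nothing about adherence on placebo.

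A third reply concerns size. A reader might take 50% as the typical score for alternate-day dosing. It requires that regimen for essentially the whole phase. Protocol 11.1.3.1 presents reduced frequency as something to try, with return to daily dosing as tolerated, and Protocol 7.4.2 calls pruritus less common in PSC than in PBC. Shorter use costs less, as the table in the working shows.

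**Conclusion.** The point holds for a reported figure. On the plain reading of SAP 10.1.1 with the protocol's own definition of a drug holiday, a fully adherent subject on a permitted alternate-day regimen scores about 100 × (1 − f/2)%. This assumes that the denominator is calendar days on treatment less holidays. That partial daily dosing can score 100% is a weaker conclusion, because it depends on the undefined meaning of a consumed day.

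A reader might go further and infer that the primary result is at risk. It is not. Compliance is only summarised descriptively, no analysis population in SAP section 7 sets a compliance threshold, the primary analysis is by randomised arm in the ITT population, and the exposure-response plots use AUC rather than compliance. No estimate or p-value changes. The consequence is a table that can present a tolerability-driven regimen change as non-adherence. It should be corrected before database lock, but it does not threaten the trial's conclusions. The point concerns the metric only, not which dosing regimen is right.

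**What to change.** Replace the formula in SAP 10.1.1 with tablets taken (dispensed minus returned) divided by tablets prescribed, × 100.

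- Let tablets prescribed follow the regimen in force each day, including prescribed non-daily dosing, drug holidays and non-titration.
- Calculate the ratio separately for the 1.5 mg-size and 5 mg-size tablets. A single pooled ratio would give 75% for Weeks 12–24 in the worked example, against 50% of the active dose.
- Report it for Day 1 to Week 12, Weeks 12 to 24, and overall.
- State a convention for bottles that are not returned.
- Keep the alternate-dosing and total-mg summaries, so that tolerability-driven changes stay visible.

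The cost is SAP wording and a derived variable for each tablet size. No new data are needed: returned tablets are counted at the on-site double-blind visits after Day 0, the two sizes come in separate bottles (Protocol 9.1), non-daily regimens are recorded in the CRF, and an accountability listing is already planned (SAP Appendix A, listing 16.2.5.1). The small downside is the unreturned-bottle convention, which the day-count formula does not need.
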